### **2.3 Randomization Procedure**

Each client who consents to be part of the study will receive a scratch card that will indicate their intervention arm (i.e. the combination of prices at which they will be offered an RDT and a conditional ACT). We will stratify on retail outlet to ensure that each of the 10 outlets has a similar number of clients who are assigned to the four study arms (approximately 21 per arm, per retail outlet for a total sample of 210 per arm). Due to the nature of the interventions, it is not possible to blind participants and research assistants to the allocation received. Study statisticians will be blinded during the analysis phase. Scratch cards were allocated in batches of 100 or 60 (25 of each or 15 of each arm) and shuffled thoroughly. Batches were assigned to specific outlets based on sales volume (i.e., higher-volume outlets received larger batches of 100 cards, smaller outlets received batches of 60 shuffled cards). Participants were asked to select a card from the shuffled stack. Cards were replenished when ten were remaining.

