Although a priori we do not anticipate a significant interaction effect, we will perform an additional test to evaluate that assumption. If, as expected, a significant interaction effect is not detected, we will perform our planned tests of the main effects of each of the factors (see the first column in Table 2). Thus, we will have conducted three total significance tests, and will adjust for familywise Type 1 error rate using the Bonferroni correction ( $\alpha=0.05/3=0.0167$ ). As shown in the last column of Table 2, we would still have 80% power to detect the expected effect sizes with the total sample size of 838, given that Bonferroni correction is a conservative method of familywise error rate adjustment. We will use different error rate allocation methods to gain more power in statistical analysis. In the unlikely case that a significant interaction effect exists, we will instead test the conditional effects of each of factor and adjust for Type I error accordingly (as described in section 4.2; see Table 3).

**Table 2:** Expected effect sizes for the main comparisons of interest and sample size required for 80%,

Description of Comparison	Expected Increase in Testing Uptake	Total sample size required for 90% power ( $\alpha=0.05$ )	Total sample size required for 85% power ( $\alpha=0.0167$ )	Total sample size required for 80% power ( $\alpha=0.0167$ )
Effect of reducing conditional ACT price from \$0.40 (67% subsidy) to \$0.00 (100% subsidy)	10 percentage points (from 67.5% to 77.5%)	838	936	832
Effect of reducing RDT price from \$0.40 (no subsidy) to \$0.20 (50% subsidy)	15 percentage points (from 65% to 80%)	374	414	370

85%, and 90% power to detect those effect sizes (with two-tailed Type 1 error set at 0.0167 and 0.05, and using standard methods for two-sample comparison of proportions).

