where  $Y_{ij}$  is an indicator of whether client  $j$  in outlet  $i$  ( $j=1, \dots, 84$ ;  $i = 1, \dots, 10$ ), chose to get tested for malaria in the retail outlet ( $=1$  if tested,  $0$  otherwise) and  $E(Y_{ij})$  is its expected value.  $\text{RDT\_SUBSIDY\_50\%}_{ij}$  is an indicator for whether the client received the lower RDT price of \$0.20 ( $=1$  if they received the offer of an RDT at \$0.20,  $=-1$  if they received the offer of an RDT at \$0.40) and  $\text{ACT\_SUBSIDY\_100\%}_{ij}$  is an indicator for whether the client received the higher ACT subsidy ( $=1$  if ACT price conditional on a positive test is \$0,  $=-1$  if ACT price conditional on positive test is \$0.40). Therefore,  $\text{RDT\_SUBSIDY\_50\%}_{ij} * \text{ACT\_SUBSIDY\_100\%}_{ij}$  represents an interaction term for clients who receive both the higher RDT and ACT subsidies or both the lower RDT and ACT subsidies ( $=1$  in two situations: a. RDT is offered at \$0.20 and ACT is offered at \$0 conditional on a positive test or b. RDT is offered at \$0.40 and ACT price conditional on positive test is \$0.40,  $=-1$  otherwise).  $\mathbf{w}_{ij}$  is a vector of potential confounder variables (e.g., age, gender, wealth, education) to account for possible imbalances between study arms. To account for possible clustering due to multiple individuals being randomized within 10 different (randomly-sampled) outlets we will use a generalized estimating equations (GEE) approach with

exchangeable working covariance matrix, robust standard errors (to correct for model misspecification due to specifying a Poisson distribution) and finite-sample correction (to obtain unbiased standard errors estimates using the Kauermann-Carroll method)[4, 5]. Regression diagnostics, including residual plots, will be used to verify model assumptions. Because all secondary outcomes are binary, we will use the same modelling approach to compare these outcomes.

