In the primary model (Model 1),  $\beta_0$  represents the overall mean of log-mean level (i.e. log-proportion) of testing uptake across all treatment arms.  $\beta_1$  represents the deviation of the log-proportion of testing uptake from the overall mean when reducing the price of the RDT from \$0.40 to \$0.20, averaged across ACT subsidy levels, while  $\beta_2$  represents the deviation of the log-proportion of testing uptake from the overall mean when reducing the price of the ACT, conditional on a positive test, from \$0.40 to \$0, averaged across RDT subsidy levels.  $\beta_3$  represents the interaction effect between the two price changes: it is the additional effect on log-proportion of testing uptake when both commodities are offered at the lower price level or higher price level, and also the negative additional effect if only one of RDT and ACT is offered at a lower price level. Relative risk ratio for the average effect of each of the price reductions cannot be obtained due to the nature of the model. However, an approximation of it can be obtained by exponentiating the parameters and deriving corresponding 95% confidence intervals.

In the secondary model (Model 2),  $\beta_0$  represents the overall mean of the proportion of testing uptake across all treatment arms.  $\beta_1$  represents the deviation of the proportion of testing uptake from the overall mean when reducing the price of the RDT from \$0.40 to \$0.20, averaged across ACT subsidy levels, while  $\beta_2$  represents the deviation of the proportion of testing uptake from the overall mean when reducing the price of the ACT, conditional on a positive test, from \$0.40 to \$0, averaged across RDT subsidy levels.  $\beta_3$  represents the interaction effect between the two price changes: it is the additional effect on the proportion of testing uptake when both commodities are offered at the lower price level or higher price level, and also the negative additional effect if only one of RDT and ACT is offered at a lower price level. Absolute risk differences and corresponding 95% confidence intervals can be obtained by directly evaluating the model parameters.

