Our two primary goals are to determine whether RDT uptake increases significantly when the price of the RDT is reduced from \$0.40 (no subsidy) to \$0.20 (a 50% subsidy), averaged over the ACT price levels (i.e. the main effect), and when the price of the ACT conditional on a positive test is reduced from \$0.40 to \$0 (67% subsidy vs 100% subsidy), averaged over the RDT price levels (i.e. the main effect). That is, we wish to test for the main effects of these two commodities. These can be evaluated by testing the null hypotheses  $H_0: 2\beta_1=0$  and  $H_0: 2\beta_2=0$ , with 2% Type 1 error rate respectively. Although, a priori, we hypothesized no statistical interaction

on absolute scale in our sample size calculations, a secondary aim is to determine whether the effect of each of the price changes depends on the price of the other commodity. This can be tested by evaluating the null hypothesis  $H_0: \beta_3=0$  in model 2 on the absolute scale with 1% Type 1 error rate. If this effect is statistically different from zero, we will report the effect of the price reductions of each commodity conditional on the price of the other commodity, with a Type 1 error rate of 1% respectively. If, however, as we expect, there is no statistically significant or scientifically meaningful interaction (i.e.  $\beta_3$  is close to zero), we will estimate the average effects from a model with interaction to match the study design with a Type 1 error rate of 2% respectively. The allocation of Type 1 error rate is based on the a priori importance of the hypothesis tests and provides more power than the conservative strategy employed in our sample size calculations (section 2.4). Contrasts of interest are summarized in Table 3.

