In the unlikely case that the modified Poisson models fail to converge, we will use a logit-link in order to estimate odds ratios as the measure of effect. As mentioned before, we will additionally provide estimates of absolute effects (risk differences) in order to provide an intuitive measure of the potential public of the interventions. Such an approach is recommended by the CONSORT statement on reporting of cluster randomized trials [6]. These risk differences will be estimated by changing the log-link to an identity link. If convergence is not achieved, we will consider an alternative specification using a normal distribution with identity link and the same approach of using robust standard errors to account for model misspecification. We will fit all models using Stata version 15 [7].

Table 3: Contrasts of interest	Population	Contrast	Alpha
Interaction effect			
(0a) The interaction effect of RDT subsidy and conditional ACT subsidy.	Full cohort	$2\beta_3$ in Model 2	0.01
Primary outcomes (given no significant interaction effect)			
(1a) Effect of RDT subsidy on the uptake of testing, averaged over the ACT price levels.	Full cohort	$2\beta_1$ in Model 1	0.02
(1b) Effect of conditional ACT subsidy on the uptake of testing, averaged over the RDT price levels.	Full cohort	$2\beta_2$ in Model 1	0.02
Primary outcomes (given strong interaction effect)			
(2a) Effect of RDT subsidy on the uptake of testing, given no conditional ACT subsidy.	No conditional ACT subsidy	$2\beta_1-2\beta_3$ in Model 1	0.01

(2b) Effect of RDT subsidy on the uptake of testing, given conditional ACT subsidy.	Conditional ACT subsidy	$2\beta_1+2\beta_3$ in Model 1	0.01
(2c) Effect of conditional ACT subsidy on the uptake of testing, given no RDT subsidy.	No RDT subsidy	$2\beta_2-2\beta_3$ in Model 1	0.01
(2d) Effect of conditional ACT subsidy on the uptake of testing, given RDT subsidy.	RDT subsidy	$2\beta_2+2\beta_3$ in Model 1	0.01

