### **5.3 Level of Randomization**

In Aim 1, we randomize at the individual level because we are testing the effect of RDT and ACT prices on individual clients' decision about whether to get tested for malaria. For a given sample size of clients, randomizing at the individual level gives us greater statistical power for detecting effect sizes than randomizing at a higher level such as the retail outlet.

Since clients generally enter the shop one at a time, we do not expect there to be any spillovers between the treatment arms (i.e. we do not expect that offering a client one combination of subsidies will affect the decision-making of a client assigned to another treatment arm within the same shop). Moreover, since the study will be administered by the research assistant (and not the shopkeeper), this should minimize the concern that individual testing decisions might be influenced by the shopkeeper. Randomizing at the individual level also reduces the likelihood that clients will visit specific retail outlets in order to get the highest subsidy levels of the two commodities.

We do not expect there to be significant clustering of the outcome by retail outlet because the 10 retail outlets will be chosen to have similar characteristics in terms of location, size, client load, length of time the shop has been open, inventory, and qualifications of the drug shop owner. We will further minimize clustering by having a research assistant perform the RDT (rather than the shopkeeper), rotating the research assistants across the 10 outlets, and by ensuring that the intervention is delivered in a consistent manner across all outlets. Based on our ongoing work in the region, we expect at most an intra-class correlation coefficient of approximately 0.008, which would still give us 80% power to detect our expected effect sizes. Since we only have 10 shops (i.e. 10 clusters) we will need to use finite-sample correction methods to estimate parameter standard errors. Specifically, the Kauerman-Carroll approach is recommended when the number of individuals per unit is similar across all units [4, 5].

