As our interventions are randomly assigned at the individual level, and because we plan to enroll more than 200 clients per treatment arm, we do not expect any confounding related to individual client characteristics. However, in our main model we will include the following covariates that may affect the decision of whether to test for malaria: the age, gender, wealth, and education level of the client (if the client is under the age of 18 then we will include the education level of the parent/legal guardian). Including these covariates will account for any imbalances across the treatment groups that may occur by chance and should also increase the precision of our estimates.

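### No reference distribution is stated for tests built on 10 outlets: a normal reference runs the 2% tests at about 4.5%, while t(9) leaves ACT power near 65%, not 80%

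*SAP*

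**What the plan says.** SAP 4.2 fits modified Poisson GEE models with outlet as the cluster, an exchangeable working matrix, robust standard errors and a "finite-sample correction (to obtain unbiased standard errors estimates using the Kauermann-Carroll method"). Protocol 7.4 names the same correction. SAP 5.3 gives the reason: "Since we only have 10 shops (i.e. 10 clusters) we will need to use finite-sample correction methods to estimate parameter standard errors".

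SAP 4.2 divides a 5% familywise error rate. The two main effects are tested "with 2% Type 1 error rate respectively", and the interaction is tested at 1% in Model 2. The interaction result decides whether the averaged contrasts (1a, 1b) or the conditional contrasts (2a to 2d) are reported as primary. The ACT main effect appears in Table 3 as "1b) Effect of conditional ACT subsidy on the uptake of testing, averaged over the RDT price levels", that is 2β2 in Model 1, on the log scale. On intervals the SAP says only that "an approximation of it can be obtained by exponentiating the parameters and deriving corresponding 95% confidence intervals".

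On power, SAP 2.4 applies a Bonferroni alpha of 0.0167 and concludes that "we would still have 80% power to detect the expected effect sizes with the total sample size of 838".

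No section gives a reference distribution or degrees of freedom. In the SAP's own checklist, item 20i (non-standard methods, with alternative degree-of-freedom calculations as an example) is marked not applicable. Item 20f (including how confidence intervals are constructed) is marked as included.

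**The concern.** The SAP treats the small number of outlets as a problem of bias in the standard error. The Kauermann-Carroll correction deals with most of that bias. A sandwich standard error assembled from 10 outlet contributions is still a noisy estimate after its bias is removed, and the ratio of estimate to standard error has heavier tails than a normal variable. The reference distribution therefore sets both the real error rate and the real power.

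The two obvious choices are alternatives, and each breaks something the SAP states. A normal reference does not deliver the 2%/2%/1% split. A t reference on 9 df delivers it, but not the 80% ACT power. The choice is unwritten, so it could be made after results are seen. A non-significant ACT result would also be read against a power figure that the error-controlled analysis does not have. The ACT contrast is the exposed one, because it determined the sample size.

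**Working it through.** **Inputs.** Planned uptake by arm is 85%, 75%, 70% and 60% (SAP 2.4, Table 1), with 210 per arm and about 21 per arm per outlet (SAP 2.3), 10 outlets, and ICC at most 0.008 (SAP 2.4, 5.3). Alphas are 0.02, 0.02 and 0.01 (SAP 4.2) and 0.0167 (SAP 2.4). Assumed, not in the documents: df = 10 − 1 = 9, with 6 df as a sensitivity value.

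**1. The plan's own figures.** The formula is the two-sample Z-test with pooled variance under the null, two-sided, no continuity correction.
- ACT (67.5% vs 77.5%): total N is 834 for 90% power at 0.05 (stated 838), 936 for 85% at 0.0167 (stated 936) and 832 for 80% at 0.0167 (stated 832).
- RDT (65% vs 80%): 370, 414 and 370 (stated 374, 414 and 370).
- ACT power at N = 838 is 80.3% at alpha 0.0167. The stated 80% is correct for its method.

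**2. Error rate with a normal reference.** If the statistic follows t(9), actual size is P(|t9| > z critical value).
- Nominal 2%: P(|t9| > 2.326) = 4.5% (5.9% at 6 df).
- Nominal 1%: P(|t9| > 2.576) = 3.0% (4.2% at 6 df).
- Bound on the total: 4.5 + 4.5 + 3.0 = 12.0%, against 5%.
- A nominal 95% interval misses the true value 8.2% of the time.

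**3. Power with a t(9) reference.**
- ACT, log scale (contrast 1b): effect = ½[ln(0.85/0.75) + ln(0.70/0.60)] = 0.1397. SE = √{¼ Σ (1−p)/(210p)} = 0.0437. Noncentrality = 3.195.
- ACT, risk-difference scale: effect = 0.10. SE = √{¼ Σ p(1−p)/210} = 0.0302. Noncentrality = 3.314.
- RDT, log scale: effect = ½[ln(0.85/0.70) + ln(0.75/0.60)] = 0.2086. Noncentrality = 4.773.

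| Contrast and scale | Alpha | Normal | t(9) | t(6) |
|---|---|---|---|---|
| ACT, log | 0.02 | 80.7% | 64.9% | 56.0% |
| ACT, log | 0.0167 | 78.9% | 61.4% | 51.9% |
| ACT, log | 0.05 | 89.2% | 81.1% | 75.9% |
| ACT, risk difference | 0.0167 | 82.1% | 65.1% | 55.4% |
| RDT, log | 0.02 | 99.3% | 95.4% | 90.4% |

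**4. Simulation of the planned model.** Modified Poisson GEE, effect coding with interaction, exchangeable matrix, Kauermann-Carroll standard errors, 10 outlets of 84, ICC 0.008.
- 20,000 replicates, no covariates: at nominal 2% the ACT null is rejected 4.2% of the time (normal) and 1.8% (t9). ACT power at alpha 0.02 is 80.2% (normal) and 65.5% (t9).
- 8,000 replicates, four non-prognostic covariates: ACT null 4.3% and 1.8%. Interaction null at nominal 1%, identity link: 3.0% (normal) and 0.9–1.2% (t9). ACT power with t(9): 66.0% at 0.02 and 62.3% at 0.0167.
- ICC set to 0 (6,000 replicates): 4.3%, 1.8% and 66%. The cause is the number of outlets, not the strength of clustering.
- Unequal outlets, six of 100 and four of 60 (a mix assumed from the card batches, "higher-volume outlets received larger batches of 100 cards, smaller outlets received batches of 60 shuffled cards"): ACT null 4.7% and 2.0%; ACT power with t(9) 65.4% at 0.02 and 61.5% at 0.0167.

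**5. Covariate gain.** SAP 5.5 says the covariates "should also increase the precision of our estimates" but gives no figure. If they remove 5%, 10% or 20% of the variance (assumed), t(9) ACT power on the log scale is 67.4%, 70.1% or 75.7% at alpha 0.02, and 64.0%, 66.7% or 72.6% at 0.0167. All stay below 80%.

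**The case against.** The strongest reply is that the 80% is a conventional Z-test figure, labelled as such, and reproduces exactly. On that view the lower power follows from choosing t(9), which the documents never adopt, and with a normal reference power is indeed about 80%. This is accurate, but it does not rescue the plan: about 80% appears only where the 2% test really runs at over 4%. SAP 2.4 also presents the figure as the power of the planned tests.

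A second objection is that part of the fall to 61% comes from moving to the log scale. That stands. At alpha 0.0167 the log scale costs about 4 points under t(9) (65.1% vs 61.4%). On the planning scale alone, the change of reference takes power from 82.1% to 65.1%, so the reference accounts for about 17 points.

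Third, the statisticians are blinded during analysis, and the references cited for the correction might themselves specify a reference distribution. Blinding is a partial safeguard. What the references say cannot be judged here, and the SAP's text does not adopt any such rule.

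Fourth, the practical stakes are limited. RDT power is secure, and the trial's aim is to choose among four subsidy combinations, with no significance rule named for that choice. This limits the consequences but does not correct the stated error rates or the ACT power.

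**Conclusion.** The concern holds. As written, the 2%/2%/1% split and the 80% ACT power at alpha 0.0167 cannot both be true of the planned analysis. With a normal reference, the 2% tests run at about 4.5% and the 1% interaction test at about 3%. With t(9), ACT power on the log scale is about 65% at alpha 0.02 and 61% at 0.0167, so a true effect of the planned size would be missed about one time in three.

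The power figures assume 9 df, no precision gain from covariates, and no variation of the ACT effect between outlets. Fewer df or variation between outlets would lower power; useful covariates would raise it, though not to 80% over the range examined.

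Two statements survive. SAP 4.2's claim that its alpha allocation gives more power than Bonferroni remains true for the main effects (64.9% vs 61.4% for ACT). The claim of at least 80% power with ICC 0.008, read at alpha 0.05, also holds at 9 df, but narrowly: 81.1% on the log scale, falling to 75.9% at 6 df. SAP 5.3 repeats that claim without giving an alpha.

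**What to change.** Before unblinding:

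- Add one sentence to SAP 4.2 and a note to Table 3: all Table 3 contrasts and their confidence intervals use Kauermann-Carroll standard errors with a t reference on 9 df (10 outlets minus one).
- In SAP 2.4, keep the Z-test figures as the basis of the sample size, and add that ACT power under the planned GEE is about 61% at alpha 0.0167 and about 65% at the alpha of 0.02 actually used. State the scale and the assumptions of no covariate gain and no variation of the ACT effect between outlets.
- Keep the GEE as primary, since it matches the population-averaged target in SAP 5.5.
- Optionally, add a sensitivity analysis with outlet as indicator terms and individual-level robust standard errors. Its inference is limited to the 10 sampled outlets, and it can over-reject if effects vary by outlet.

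The cost is one sentence, one restated power figure and one line of code, with no change to data collection or sample size. The stated ACT power becomes less favourable. The 95% intervals are about 15% wider than with a normal reference (2.262/1.960 = 1.15), and the 2% critical value rises from 2.326 to 2.821.
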